Prior to statistical analyses, the data will be inspected to determine the advisability of scale transformation to normalize distributions or reduce variance heterogeneity (e.g., logarithmic or power transformations) and to identify missing data, outliers, or other unusual features that might bias results. Where multiple measures may overlap or be redundant, preliminary analyses will explore whether it is possible to reduce these using techniques from scale development such as factor analyses. Preliminary analyses are also performed to compare treatment groups on descriptive and clinical characteristics at baseline to ensure randomization has succeeded. If there are significant differences between the treatment groups at baseline we will create propensity scores and include them in all further analyses as covariates to compensate for potential bias. We will also test if there are significant site effects, and if necessary we will include a site variable in the mixed linear model analysis, and model time as nested in subjects and subjects nested in sites.

To address concerns about excessive Type I error rates, the principal analyses are designed to answer clearly stated major research hypotheses, and are based on well-specified dependent variables. The samples are large enough to expect that confidence limits may be reasonably narrow, and findings may be robust enough to permit conservative adjustments of p-values for multiple testing. Bonferroni and other adjustments are necessarily somewhat arbitrary as Saville notes in his argument against their use (71). Additional analyses that are exploratory will be clearly identified as such. All tests will be two-tailed at $\alpha=0.05$.

2. Attrition: Dropout from treatment does not necessarily mean participants will refuse follow-up assessments, and we will attempt to obtain full follow-up data on all enrolled participants regardless of degree of participation and include all enrolled participants in analyses when any outcome data are available (intent to treat). Attrition can compromise randomization, so preliminary analyses will compare baseline characteristics

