of subjects available for analysis at each data point with those who are missing to evaluate sampling biases. Attrition naturally lends itself to analysis using survival regression models. Rates of attrition in the treatment groups will be depicted using Kaplan-Meier curves and simple comparisons performed using the log-rank test. More detailed examination of covariates that may predict dropout will be done using proportional hazard survival regression, which permits entry of both fixed (e.g., baseline status or descriptive-demographic characteristics) and time-dependent covariates that change over time (e.g., change in clinical status on prognostic variables). Dropout information is known for all subjects, so multiple logistic regressions can also be employed to evaluate multiple predictive factors without attention to timing of dropout. If trajectories of change on clinical outcome variables or interim (six month) data predict dropout, that would be taken into account in interpretation of the outcome analyses (e.g., sampling bias). We will compare subjects included in the analyses at any point with those who have dropped out on variables such as overall change from baseline, trajectory (slope or speed of change), and status at the last data point. There is no perfect statistical solution to missing data, but if dropout is deemed to be a possible source of bias in the analysis, we will consider additional analyses that specifically address sampling bias (e.g., two-stage modeling, propensity score stratification (72, 73)) weighted analyses or sensitivity analyses such as multiple imputation that examine the robustness of findings to assumptions about the outcomes of lost cases. As noted below, the proposed longitudinal (repeated measures) analyses are likelihood-based general (or generalized) linear mixed models, which permit missing data (see (74) for a recent, explicit comparison of five alternative data analysis approaches to the missing data problem which strongly cautions against analyses based only on complete cases and comments favorably on the use of linear mixed model methods).

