3. Repeated measures analyses: We propose to longitudinal (repeated measures) analyses to maximize the additional power we gain by observing the same subjects across 12 months.. Repeated measures analyses permit contrasts at each time point, and also describe and compare trajectories of change (trends), speed and durability of effects. We will also conduct separate cross-sectional to provide outcome data for ongoing safety review, interim progress reports, study oversight and conduct.

The primary design for longitudinal (repeated measures) analyses of continuous outcome scales will be a 2-group (treatment) mixed general linear model of timepoints nested within participants. This is very general linear model that permits flexibility in specifying the nature of the covariances among the dependent measures, allows time-dependent, within and between subject covariates, and permits incomplete (i.e., missing) data. Analyses of trends across the monthly assessments will be done using growth curve model within the mixed model analysis of covariance design with repeated measures described above. We propose to model a linear trend of time unless inspection clearly suggests nonlinearity. By fitting a slope over time (and intercept) for each participant who has baseline and at least one other measure, this method makes good use of all the data, and is robust even if some of the some measures are missing. The use of the mixed general linear model for all cross-sectional and linear hypotheses ensures that results will be comparable across different analyses and provide a framework to include group, person and time-specific covariates if it becomes necessary. The preliminary analyses have shown that this analysis strategy provides meaningful results even with partial data and suggests that we will exceed the originally projected power.**4. Stratification:** Randomization will be stratified by type of antipsychotic and presence of mood stabilizer medication (e.g., depakote, lithium) to assure balance on olanzapine and clozapine by randomizing within three strata – olanzapine, clozapine, and all other antipsychotics -- using three separate randomization lists. Because such stratification can adversely affect statistical power by creating artificially comparable (and heterogeneous) groups, two dummy variables coding olanzapine and clozapine at baseline will be included in all analyses as covariates.

4. Statistical Plans:

Primary Hypotheses:

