a) SMI patients with antipsychotic associated obesity who participate in a behavioral intervention that includes classes on Lifestyle Balance will gain more knowledge (i.e., greater change scores on before/after survey test instrument) about general health issues (e.g., nutrition, importance of exercise.) than a control group receiving “usual psychiatric care”.

b) SMI patients with antipsychotic associated obesity who participate in a behavioral intervention program will achieve better cardiovascular (e.g., sustained weight loss, better glucose tolerance, improved lipid profiles, and improvement in other biological measures, e.g. insulin and c-reactive protein) and mental health (e.g., improvements in general measures of psychopathology, subjective quality of life, etc) outcomes than the control group. A larger proportion of patients who take the Lifestyle Balance classes will actually make lifestyle

changes (objectively measured by food and exercise diaries) than patients in the usual care group given ordinary counseling.

c) A larger proportion of patients who take the Lifestyle Balance classes will actually make lifestyle changes (objectively measured by food and exercise diaries and exit interviews) than patients in the usual care group given ordinary counseling. Analysis plan: For all hypotheses concerning the effects of the treatment program use analysis of repeated measures using the assessments at baseline, 8 weeks, 6 months, and 12 months. These analyses will provide information about maintenance of treatment effects. We will use a mixed general linear model with timepoints nested within patients. For hypothesis (c) we will adapt the mixed general linear model to dichotomous data by using a logistic link function to model the likelihood of life style changes. We will include all patients with at least one post-baseline data point in the analysis to maximize power. We will also consider the appropriateness of linear growth curve mixed effects models, i.e., fitting an intercept and linear slope for each treatment group as fixed effects, and separate intercepts and linear slopes for each patient as random effects. Analyses of linear trends over time with a single df effect are often more powerful tests of differences in trends than multiple df profile contrasts across the separate time points.

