General linear mixed effects models permit missing data but assume that data are missing at random. We will explore this assumption by comparing attrition rates in the study groups, and by comparing patients with and without post-treatment data on baseline scores and other baseline characteristics. If missing at randomness does not seem like a valid approach we will use multiple imputation based on different models of missingness to determine the degree of potential bias due to the way we approach the problem of missing data. Based on our experience with similar data we don't expect the data to violate missingness at random, but if it does we will use the results of the multiple imputation based on the EM algorithm to derive confidence intervals for our parameter estimates.

For Primary Hypothesis C, intraclass correlations will be run to assess the concurrent validity of the BPSS (compared to the WHO-QOL) to examine the relationship between study participation and biopsychosocialspiritual wellness.

Secondary Hypotheses:

a) Negative and Cognitive Symptoms will affect weight loss. Specifically we hypothesize: i.) High levels of negative symptoms as rated by the BPRS negative symptom cluster will correlate negatively with weight loss; ii.) Motivation to change level will impact weight loss directly; iii.) High levels of cognitive impairment as measured by the BPRS cognitive cluster will correlate with low weight loss, and; iv.) Insight into illness (as measured by the SAIQ) will correlate directly with weight loss. v.) High motivation as measured by the URICA will correlate with successful weight loss

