It provides valid statistics even in cases where there are more potential predictors than observations, and allows us to include all demographic, psychosocial, psychiatric and medical data known at baseline as potential predictors. The results of this analysis will suggest which patients are most likely to profit from further interventions, and it will also characterize the most at risk patients.

c) Subjects will continue to give meaningful, informed consent to participate throughout the study. They will see no significant decrease in their score on the informed consent quiz given every 6 months.

Analysis plan: A general linear model (GLM): ANOVA will be performed to compare the informed quizzes score results at 0, 6, and 12 months during the subjects' participation in the study.

5. Power Analysis: All calculations are based assuming a conventional medium effect size ($f=.25$, Cohen 1988); and a two-tailed alpha set at 0.05. Tuomilehto et al. estimated the SD of weight loss at roughly 5 kg across several treatment conditions (lifestyle changes vs. control) (76). A medium effect would thus translate into a group difference of about 2.5 kg or about 5.5 pounds. With an enrollment of $N=120$ and an estimated attrition rate of 45% we expect that at least 66 subjects will provide complete the study and provide 4 data points. The power analyses below are based on a sample size of $N=66$, i.e. this is a very conservative estimate due to the fact that the mixed linear model allows us to include cases with missing values in the analyses and that while they don't provide as much information as complete cases they still provide some information and will increase power. For the between-group comparisons, $N=66$ yields power=.7199 for main differences between groups if we assume that the within subject correlation is $r=.50$. Power to test for the difference in outcome trajectories of time – our main outcome variable is 0.99, and even if the effect is as small as $f=0.15$ we will have sufficient power to distinguish between the trajectories of the two treatment groups (power=0.83) insuring that we will get significant, insuring that we Preliminary data analyses shows that these assumptions are quite conservative and that effect sizes seem to be slightly larger than projected, suggesting that the final power will exceed the estimates presented here.

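### The primary mixed model leaves out randomised patients who have only a baseline value; keeping them costs nothing and removes a possible bias under missing at random

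*Combined protocol and SAP*

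**What the plan says.** Three places in section V.N bear on who is analysed.

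- **V.N.2, Attrition.** The plan will try to follow everyone, whatever their participation, and will "include all enrolled participants in analyses when any outcome data are available (intent to treat".
- **V.N.3, Repeated measures analyses.** The growth curve fits a slope and intercept "for each participant who has baseline and at least one other measure".
- **Statistical Plans, analysis plan for the primary hypotheses.** "We will include all patients with at least one post-baseline data point in the analysis to maximize power". The model is to "use analysis of repeated measures using the assessments at baseline, 8 weeks, 6 months, and 12 months", so baseline is one of the modelled values.

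On missing data, V.N.2 relies on likelihood-based mixed models and cites a comparison that "strongly cautions against analyses based only on complete cases". V.N.5, Power Analysis, says of incomplete cases that "while they don't provide as much information as complete cases they still provide some information and will increase power". Statistical Plans will examine missing at random by "comparing patients with and without post-treatment data on baseline scores and other baseline characteristics". If that assumption does not seem valid, "we will use multiple imputation based on different models of missingness to determine the degree of potential bias".

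No analysis of all randomised patients, primary or sensitivity, is firmly specified.

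**The concern.** A likelihood model that has baseline among its responses can use a patient who has nothing else. That patient helps estimate the arm's baseline mean and, through the correlation between visits, corrects the later means for who was lost. Requiring a post-baseline value discards this information and selects patients after randomisation.

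The selection is harmless if early loss is unrelated to baseline, or related to it in the same way in both arms. It need not be so here. The trial is open (V.A), and only the program arm has classes, diaries and goal sheets in the first eight weeks. If patients with high baseline values leave one arm early, those who remain start lower, and their change from baseline is shifted. The estimated effect could then be wrong in either direction, although the missing-at-random assumption holds.

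The reach depends on the measure. In the Schedule of Events the knowledge quiz, BPRS and laboratory tests are first repeated at week 8. The Quality of Life Scale is given only at baseline and one year, so for it the rule amounts to a complete-case analysis. Weight is taken at every visit, including weeks 1 to 7, and is least exposed.

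**Working it through.** **1. The plan's own figures (V.N.5).** Inputs: N = 120, 45% attrition, 4 time points, r = 0.50, two-sided alpha 0.05, f = 0.25 or 0.15.

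- Completers: 120 × (1 − 0.45) = 66.
- Between groups: λ = f²·N·m / (1 + (m−1)r) = 0.0625 × 66 × 4 / 2.5 = 6.6, with df 1 and 64. Power is 0.716 (plan: 0.7199).
- Group by time: λ = f²·N·m / (1 − r), with df 3 and 192. For f = 0.25, λ = 33.0 and power is 0.999 (plan: 0.99). For f = 0.15, λ = 11.88 and power is 0.828 (plan: 0.83).

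The figures reproduce. They rest on 66 completers, so the inclusion rule does not affect them.

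**2. Power under three analysis sets.** The test is of the 12-month change contrast, with d = 0.5, r = 0.5 at all visit pairs, and arm-specific means at 0, 2, 6 and 12 months. Assumptions not in the documents: 1:1 allocation (33 completers per arm), and the timing of loss among the 120 − 66 = 54 dropouts. Those with some follow-up are split evenly between last visit at month 2 and at month 6. Power = Φ(d/SE − 1.96), with SE from the generalised least squares information.

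Check for completers: the variance of change is 2(1 − 0.5) = 1, so SE = √(2/33) = 0.246 and power = Φ(2.03 − 1.96) = 0.528.

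| Dropouts with baseline only | Completers | Plan's rule | All with a baseline |
|---|---|---|---|
| 0 | 0.528 | 0.602 | 0.602 |
| 18 | 0.528 | 0.584 | 0.596 |
| 27 | 0.528 | 0.574 | 0.593 |
| 54 | 0.528 | 0.528 | 0.578 |

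The rule beats completers whenever some dropouts have follow-up. It never beats keeping everyone. The gain from keeping everyone is 0 to 5 points, and 1 to 2 points when 18 to 27 have baseline only.

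**3. Bias.** With baseline as a response and standardised values, the expected later value given baseline b is r·b plus a constant. The mean change among retained patients is therefore shifted by −(1 − r) × (shift in the retained baseline mean).

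Assumptions: 20% lost before the first follow-up in each arm, with log-odds of loss rising by 0.7 per SD of baseline.

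- Those lost average +0.52 SD at baseline, so those retained average −0.20 × 0.52 / 0.80 = −0.13 SD.
- Dependence in one arm only, r = 0.5: 0.5 × 0.13 = 0.065, about 0.06 SD.
- Opposite dependence in the two arms: 2 × 0.065 = 0.13 SD.
- r = 0.95: 0.05 × 0.13 = 0.0065 (one arm) and 0.013 (opposite), about 0.01 SD.
- Same dependence and same loss in both arms, or no dependence: 0.
- All baselines kept in the likelihood: about 0 in every case, by large-sample simulation.

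Range over the share lost, at r = 0.5: 0.05 SD (15% lost) to 0.14 SD (45% lost) with dependence in one arm, and 0.10 to 0.29 SD if opposite.

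**4. Kilograms, for scale only.** The 5 kg in V.N.5 is the SD of weight loss, so the visit SD is 5/√(2(1 − r)) and the one-arm bias is 0.13 × 5 × √((1 − r)/2). That is 0.13 × 5 × 0.5 = 0.33 kg at r = 0.5 and 0.13 × 5 × 0.158 = 0.10 kg at r = 0.95, or 13% and 4% of the 2.5 kg target. Weight is the measure least exposed to the rule.

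**The case against.** A reader might infer that the plan plainly contradicts its own intent-to-treat rule. The documents do not support that. The rule in V.N.2 is conditional on available outcome data. In a paragraph about follow-up this can naturally mean follow-up data, and then V.N.2, V.N.3 and Statistical Plans agree. They conflict only if a baseline value counts as outcome data.

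A reader might also infer that patients are dropped to gain power, and that this cannot work. The sentence is an inclusion rule. The plan's comparator is completers, and against them the rule does raise power (0.528 to 0.584 with 18 excluded).

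Nor is everyone who leaves during the class phase removed. V.N.2 separates leaving treatment from loss to follow-up and will attempt assessments on all. For weight, visits in weeks 1 to 7 may also supply a later value, although the four-visit list in Statistical Plans leaves unclear whether they count.

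Visit schedule and contact time are matched (V.E, V.H), which makes equal dependence on baseline more plausible. The bias also disappears if baseline is a covariate, and V.N.3 does mention analysis of covariance.

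All of this stands and narrows the point. The multiple-imputation fallback does not close it. It is invoked only if missing at random is doubted, and loss that depends on an observed baseline is missing at random. The likelihood model handles such loss only if those baselines stay in.

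**Conclusion.** The point holds as a free improvement. The inclusion rule omits baseline-only patients from a model that treats baseline as a response, and the plan leaves open whether they belong to its intent-to-treat set. Keeping them never lowers power. Omitting them can bias the between-arm difference in change when early loss depends on baseline differently by arm: about 0.06 SD (one arm) to 0.13 SD (opposite) at 20% loss and r = 0.5, and about 0.01 SD at r = 0.95. The bias is zero when the dependence is equal or absent, or when baseline is a covariate.

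The loss pattern, its strength, 1:1 allocation and the higher correlation are assumptions. The documents give only 45% total attrition and r = 0.50. They do not show that differential loss will occur, so a reader should not take the bias as established.

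It matters most for the Quality of Life Scale, where up to 54 of 120 patients could lack the one-year value if follow-up after dropout fails. Next come the measures first repeated at week 8. It matters least for weight.

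**What to change.** In Statistical Plans, replace the inclusion sentence with one saying that all randomised patients with a baseline or any later value enter the likelihood model in their assigned arm, with baseline as a response. In V.N.3, remove the condition that a patient needs baseline and one further measure. In V.N.2, say that a baseline value counts as outcome data.

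Leave the comparison of patients with and without post-treatment data, and its multiple-imputation fallback, as they are. They address departures from missing at random, which this change does not.

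The cost is a few sentences. No new data are needed, and no power is lost.

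### The repeated-measures model leaves each arm's baseline mean free, so the treatment contrast is unbiased but less precise than the same data allow

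*Combined protocol and SAP*

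**What the plan says.** All references are to section V.N of the combined protocol and SAP.

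- **Statistical Plans, Primary Hypotheses, Analysis plan.** Treatment effects are tested by "analysis of repeated measures using the assessments at baseline, 8 weeks, 6 months, and 12 months", in a mixed model with timepoints nested within patients. Baseline is therefore a response, not a covariate. The plan will also consider a linear growth curve, "fitting an intercept and linear slope for each treatment group as fixed effects", with random intercepts and slopes per patient.
- **Repeated measures analyses.** A linear time trend is the default unless the data clearly look nonlinear. The design is called a mixed-model analysis of covariance, but the baseline outcome is not named as the covariate. The Stratification paragraph that follows names two covariates for all analyses, the olanzapine and clozapine indicators.
- **General Data Analysis Issues.** Propensity scores are added as covariates only if the arms differ significantly at baseline.
- **Power Analysis.** The trajectory difference is called the main outcome: "Power to test for the difference in outcome trajectories of time" is given as 0.99.

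**The concern.** Time zero precedes treatment and patients are randomized, so any observed baseline difference between arms is chance. A model that estimates a separate baseline mean for each arm subtracts that chance difference in full. The group-by-time contrast then becomes a difference of raw changes from baseline. A model with one common baseline mean subtracts only the part that the correlation justifies, which is what a baseline-adjusted analysis does.

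What is at stake is precision: wider confidence intervals and lower power for the test that the plan relies on, in a trial that expects to lose 45% of its patients. The wording also leaves room for two analysts to fit different models, because analysis of covariance is mentioned without saying whether the baseline outcome is a covariate.

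**Working it through.** **Inputs (Power Analysis unless noted).** The test uses "a two-tailed alpha set at 0.05". Sample size: "With an enrollment of $N=120$ and an estimated attrition rate of 45% we expect that at least 66 subjects"; 1:1 allocation is assumed, so 33 per arm. The cited study "estimated the SD of weight loss at roughly 5 kg across several treatment conditions". Difference: "A medium effect would thus translate into a group difference of about 2.5 kg or about 5.5 pounds". Within-subject correlation r = .50 is stated only for the between-group comparison. Visits are at months 0, 2, 6 and 12 (Analysis plan). Assumed, because the plan does not say: equal correlation between all visits, complete data on 66 patients, and the shape of the effect over time. The 5 kg is an SD of change; it equals the SD at a single visit only when r = .50, since the change variance is 2(1−r)SD².

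**Step 1: the plan's own power figures.** For N = 66 and m = 4 measurements:
- Between groups: λ = f²Nm/[1+(m−1)r] = 0.0625×264/2.5 = 6.6; F on 1 and 64 df gives 0.716 (stated 0.7199).
- Group by time, f = .25: λ = f²Nm/(1−r) = 0.0625×264/0.5 = 33; F on 3 and 192 df gives 0.999 (stated 0.99).
- Group by time, f = .15: λ = 0.0225×264/0.5 = 11.88; power 0.828 (stated 0.83).

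All three reproduce within 2 points.

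**Step 2: month 12 against baseline.**
- Free baseline means: variance = 2(1−r)·SD²·(2/n) = 1.00×25×2/33 = 1.515; SE 1.23 kg.
- Common baseline mean: variance = (1−r²)·SD²·(2/n) = 0.75×25×2/33 = 1.136; SE 1.07 kg.
- Ratio = (1−r²)/[2(1−r)] = (1+r)/2 = 0.75, a 25% fall in variance, equivalent to 66/0.75 = 88 completers instead of 66.
- Power for 2.5 kg (64 df): 0.52 to 0.64.

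This step needs no effect shape. It applies directly to the Quality of Life Scale, which the Schedule of Events collects only at baseline and month 12: at d = 0.5 and r = .50 the power is again 0.52 against 0.64.

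**Step 3: group-by-time tests.** Generalized least squares, 33 per arm, SD 5 kg, r = .50, 2.5 kg at month 12:

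| Assumed effect shape | 3-df test, free → common | Linear slope test, free → common |
|---|---|---|
| Linear divergence | 0.418 → 0.506 | 0.580 → 0.672 |
| 1.25 kg at week 8, 2.5 kg from month 6 | 0.484 → 0.659 | 0.519 → 0.704 |
| Full effect from week 8 | 0.523 → 0.747 | 0.339 → 0.602 |

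**Step 4: why the last slope entry is not all noise reduction.** The slope SE, expressed over 12 months, falls from 1.14 to 1.02 kg in every row. In the last row the fitted 12-month difference also moves, from 1.79 to 2.31 kg (truth 2.5), because a straight line is being fitted to a step. With the estimate held at 1.79 kg, the smaller SE alone takes power from 0.34 to about 0.41, or 7 points of the 26.

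**Step 5: sensitivity.**
- *Effect size.* The interaction f = .25 behind the stated 0.99 corresponds to a month-12 difference of 2f divided by the SD of the shape over the four visits: 0.5/0.382 = 1.31 SD (6.5 kg) if linear, 0.5/0.433 = 1.15 SD (5.8 kg) if a step. There the gain is 0.1 points (3-df) and 0 to 5.4 points (slope). At f = .15 the 3-df gain is 7.7 to 13.7 points.
- *Correlation*, holding the SD of change at 5 kg, from linear divergence to step: the 3-df gain is 4.4 to 12.0 points at r = .7 and 1.2 to 3.6 at r = .9; the slope gain is 4.7 to 13.2 and 1.3 to 3.7.

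**Step 6: which constrained model.** If the effect grows linearly to month 6 and then plateaus at 2.5 kg, a common intercept with linear slopes gives a fitted 12-month difference of 2.69 kg. The visit-mean model with a common baseline gives 2.50 kg in every shape tried.

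**The case against.** **No error is shown.** A mixed model with free baseline means is standard, unbiased under randomization, and keeps its Type I error. This stands: the point concerns efficiency, not validity.

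**The size depends on inputs that the plan does not give.** A reader might infer a loss of 9 to 26 points at the plan's own inputs. The documents do not support that. The effect shapes and equal correlation are assumptions, r = .50 is not stated for the trajectory test, the loss at the plan's own f = .25 is 0 to 5 points, and most of the 26 comes from fitting a line to a step, which the plan's check for nonlinearity should catch.

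**For body weight, r is probably well above .50.** The men in Pilot Study 1 were 26% normal weight, 37% overweight and 37% obese. Under normality that implies a BMI SD of about 5.1, or about 3.7 if truncated at 25. At assumed heights of 1.65 to 1.85 m the weight SD is roughly 10 to 17 kg, so r = 1 − 25/(2·SD²) is about .88 to .96. That sample differs from this trial's, so this is only indicative, but it puts the gain for weight at a few points or less.

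**More visits may be used.** The growth curve is meant for the monthly assessments, and weight is taken at every visit. With all 19 scheduled times, r = .50 and 2.5 kg, slope power moves only from 0.979 to 0.985 under linear divergence, and from 0.81 to 0.91 if the effect is full by week 8.

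**The text may be read too firmly.** The growth curve is a model to be considered, and analysis of covariance is mentioned. A reader might also infer that the plan ignores baseline; it does not, because baseline is the first response and informs every slope. What remains is that neither a common baseline mean nor the baseline outcome as covariate is specified, and that both model forms leave the arms' baseline means free.

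**Conclusion.** The point holds as one of precision. As described, the model estimates a baseline mean for each arm, and randomization allows one common mean. At r = .50 with equal correlation, 33 completers per arm and SD 5 kg, the month-12 contrast has a standard error of 1.23 kg where 1.07 kg is available, and power of 0.52 where 0.64 is available for a 2.5 kg difference. The 3-df test forgoes about 9 points (linear divergence) to 22 points (full effect by week 8).

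These figures rest on the assumptions listed in the working. The gain is negligible to about 5 points at f = .25 and about 1 to 4 points at r near .9. It therefore matters most for outcomes with moderate correlation between visits, and probably little for weight. The plan gives no outcome-specific correlations.

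The calculation should not be read as showing that the stated 0.99 is miscalculated, since that figure reproduces at f = .25. The mismatch between that f and a 2.5 kg difference is a separate matter.

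**What to change.** In the Analysis plan under Statistical Plans, Primary Hypotheses, specify for each continuous outcome a repeated-measures model with visit means, arm-by-visit terms at the post-baseline visits only, and no arm term at baseline. Fitting the post-baseline visits with the baseline outcome as a covariate is an acceptable alternative. State that the month-12 arm difference from this model is the reported treatment effect.

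If a linear growth curve is also fitted, give it a common fixed intercept and label it a supplementary trend test, because its month-12 difference is biased when the effect is not linear.

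Cost: one line of SAP text and one fewer parameter in the model. It uses measurements already scheduled and needs no further patients.
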